6.3.8. Time Period and Frequency of Detecting AEs and SAEs

The investigator or site staff is responsible for detecting, documenting, and reporting events that meet the definition of an AE or SAE.

Adverse events and SAEs will be collected from the start of study treatment and until the follow-up contact (see Section [6.3.10](#)) at the time points specified in [Table 5](#).

Medical occurrences that begin prior to the start of study treatment but after obtaining informed consent may be recorded on the Medical History/Current Medical Conditions section of the eCRF. Additionally, if a condition with a start date predating Day 0 (Screening) is subsequently discovered, the condition should be recorded in the Medical History eCRF.

Any SAEs assessed **as related** to study participation (e.g., protocol-mandated procedures, invasive tests, or change in existing therapy) or related to a GSK product will be recorded from the time a subject consents to participate in the study up to and including any follow-up contact.

All SAEs will be recorded and reported to GSK/PPD within 24 hours, as indicated in Section [6.3.11](#).

Investigators are not obligated to actively seek AEs or SAEs in former study subjects. However, if the investigator learns of any SAE, including a death, at any time after a subject has been discharged from the study, and he/she considers the event reasonably related to the study treatment or study participation, the investigator must promptly notify GSK/PPD.

6.3.9. Method of Detecting AEs and SAEs

Care must be taken not to introduce bias when detecting AEs and/or SAEs. Open-ended and nonleading verbal questioning of the subject is the preferred method to inquire about AE occurrence. Appropriate questions include the following:

“How are you feeling?”

“Have you had any (other) medical problems since your last visit/contact?”

“Have you taken any new medicines, other than those provided in this study, since your last visit/contact?”

6.3.10. Follow-up of AEs and SAEs

After the initial AE/SAE report, the investigator is required to proactively follow each subject at subsequent visits/contacts. All SAEs and nonserious AEs of special interest (as defined in Section [6.3](#)) will be followed until resolution, until the condition stabilizes,

until the event is otherwise explained, or until the subject is lost to follow-up (as defined in Section 4.4.1.2). For newborns participating in the infant follow-up study, unresolved SAEs and AEs of special interest will be followed to stabilization or resolution in the long-term follow-up study. Further information on follow-up procedures is given in the SPM.

6.3.11. Prompt Reporting of SAEs and Other Events to GSK/PPD

Serious AEs, nonserious AEs related to study treatment, and liver function abnormalities meeting predefined criteria will be reported promptly by the investigator to GSK/PPD as described in Table 6 once the investigator determines that the event meets the protocol definition for that event. Additional details describing DREs not qualifying as SAEs are described in Section 6.3.7.

Table 6 Reporting of Serious Adverse Events and Other Events to GSK/PPD

Type of Event	Initial Reports		Follow-up Information on a Previous Report	
	Time Frame	Documents	Time Frame	Documents
All SAEs	24 hours	“SAE” data collection tool	24 hours	Updated “SAE” data collection tool
Cardiovascular or death event	Initial and follow-up reports to be completed within 1 week of when the cardiovascular event or death is reported	“CV events” and/or “death” data collection tool(s) if applicable	Initial and follow-up reports to be completed within 1 week of when the cardiovascular event or death is reported	Updated “CV events” and/or “death” data collection tool(s) if applicable
Nonserious adverse events related to study treatment	5 calendar days	“Adverse Reaction” data collection tool	2 weeks	Updated “Adverse Reaction” data collection tool
DRE	2 weeks ¹	DRE eCRF	2 weeks ¹	Updated DRE eCRF
Liver chemistry abnormalities				
ALT \geq 3 x ULN and bilirubin \geq 2 x ULN (>35% direct) (or ALT \geq 3 x ULN and INR>1.5, if INR measured) ²	24 hours ³	“SAE” data collection tool, “Liver Event eCRF” and “Liver Imaging” and/or “Liver Biopsy” eCRFs, if applicable ⁴	24 hours	Updated “SAE” data collection tool/“Liver Event” Documents ⁴
ALT \geq 8 x ULN; ALT \geq 3 x ULN with hepatitis or rash or \geq 3 x ULN and <5 x ULN that persists \geq 4 weeks	24 hours ³	“Liver Event” Documents (defined above) ⁴	24 hours	Updated “Liver Event” Documents ⁴

ALT = alanine aminotransferase, CV = cardiovascular; DRE = disease-related event, eCRF = electronic case report form; GSK = GlaxoSmithKline; INR = International normalized ratio, SAE = serious adverse event, ULN = upper limit of normal.

1. The study review team should determine the appropriate time frame, if one is needed, for completion of DRE eCRF pages
2. The INR measurement is not required; if measured, the threshold value stated will not apply to subjects receiving anticoagulants.
3. GSK/PPD must be contacted at onset of liver chemistry elevations to discuss subject safety.
4. Liver Event Documents (i.e., “Liver Event eCRF” and “Liver Imaging eCRF” and/or “Liver Biopsy eCRF,” as applicable) should be completed as soon as possible

The contact information for reporting SAEs is as follows:

Issue	All Countries/Regions Contact
Serious Adverse Event Reporting	24-Hour SAE Hotline: PPD SAE Fax: PPD

The method of recording, evaluating, and following up of AEs and SAEs plus procedures for completing and transmitting SAE reports to GSK/PPD are provided in the SPM. Procedures for poststudy AEs/SAEs are provided in the SPM.

6.3.11.1. Regulatory Reporting Requirements for SAEs

Prompt notification of SAEs by the investigator to GSK/PPD is essential so that legal obligations and ethical responsibilities towards the safety of subjects are met.

GSK/PPD has a legal responsibility to notify both the local regulatory authority and other regulatory agencies about the safety of a product under clinical investigation. GSK/PPD will comply with country-specific regulatory requirements relating to safety reporting to the regulatory authority, Institutional Review Board (IRB)/Independent Ethics Committee (IEC), and investigators.

Investigator safety reports are prepared for suspected unexpected serious adverse reactions according to local regulatory requirements and GSK policy and are forwarded to investigators as necessary.

An investigator who receives an investigator safety report describing an SAE(s) or other specific safety information (e.g., summary or listing of SAEs) from GSK/PPD will file it with the IB and will notify the IRB/IEC, if appropriate according to local requirements.

6.3.12. Other Safety Outcomes

6.3.12.1. Physical Examination

An admission physical examination will include at minimum maternal height, weight, and assessment of heart, lungs, abdomen, and cervical examination including dilation, effacement, and station.

A brief physical examination, assessing heart, lungs, and abdomen, at a minimum, and, if undelivered, a cervical examination at the discretion of the investigator will be performed at the face-to-face post-infusion assessment visit, following conclusion of the treatment phase.

6.3.12.2. Vital Sign Measurements

Vital signs (blood pressure, pulse rate, respiratory rate, and temperature) will be measured at the following time points during the study: Screening, Inpatient Randomized Treatment Phase, retreatment (if criteria are met, see Section 3.1.3.1), and at the

face-to-face post-infusion assessment visit. During the Inpatient Randomized Treatment Phase and during retreatment, vital signs will be assessed and recorded within the following windows relative to the start of the infusion: 15 to 30 minutes, 4 to 8 hours, 20 to 24 hours, at the end of the infusion, at the time of any dose changes, and as warranted by a medical condition. Subjects may be either in a semirecumbent or seated position. It is suggested (but not required) that oxygen saturation also be assessed at Screening and recorded in source documents.

6.3.12.3. Electronic Fetal Monitoring

Electronic fetal monitoring is required for a minimum of 6 hours from the start of the infusion or from the start of a dose increase if the following are confirmed during monitoring:

- The fetal heart rate pattern is consistently reassuring throughout the required minimum 6-hour duration of monitoring
- The contraction frequency is ≤ 2 in a 30-minute window within the last hour of monitoring.

A reassuring nonstress test (defined as meeting Category I criterion), accounting for GA expectations, is required at a minimum of every 8 hours and as needed. An additional 6 hours of electronic fetal monitoring will be required for dose interruptions that are sufficiently long as to require an additional infusion bolus of the IP.

Electronic fetal monitoring, including the fetal heart rate and fetal heart rate category, should be recorded in the eCRF at approximately the same time that maternal vital sign measurements are collected (Section 6.3.12.2). The electronic fetal heart rate tracing (paper or electronic) must be archived and retained in site records. Fetal heart rate (fetal Doppler heart rate or cardiotocography are both acceptable) will be recorded at the face-to-face post-infusion assessment visit if the subject remains undelivered. During the Delivery Phase, fetal heart rate just prior to delivery will be summarized, if available, from review of delivery records. Any fetal heart rate assessment of Category II or III according to the following criteria and based on ACOG guidelines [ACOG, 2009] will be reported as an AE of special interest on a specified eCRF in addition to the corresponding AE or SAE eCRF:

Category I fetal heart rate tracings include all of the following:

- Baseline rate: 110 to 160 beats per minute
- Baseline fetal heart rate variability: moderate
- Late or variable decelerations: absent
- Early decelerations: present or absent
- Accelerations: present or absent

Category II fetal heart rate tracings include all fetal heart rate tracings not categorized as Category I or III. Category II tracings may represent an appreciable fraction of those

encountered in clinical care. Examples of Category II fetal heart rate tracings include any of the following:

- Baseline rate
 - Bradycardia not accompanied by absent baseline variability
 - Tachycardia
- Baseline fetal heart rate variability
 - Minimal baseline variability
 - Absent baseline variability with no recurrent decelerations
 - Marked baseline variability
- Accelerations
 - Absence of induced accelerations after fetal stimulation
- Periodic or episodic decelerations
 - Recurrent variable decelerations accompanied by minimal or moderate baseline variability
 - Prolonged deceleration more than 2 minutes but less than 10 minutes
 - Recurrent late decelerations with moderate baseline variability
 - Variable decelerations with other characteristics such as slow return to baseline, overshoots, or “shoulders”

Category III fetal heart rate tracings include either of the following:

- Absent baseline fetal heart rate variability and any of the following:
 - Recurrent late decelerations
 - Recurrent variable decelerations
 - Bradycardia
- Sinusoidal pattern

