4.4.1. Withdrawal From Study

4.4.1.1. Withdrawal From Study Participation After Randomization but Prior to Investigational Product Administration

Any subject with a nonreassuring fetal heart rate pattern, a re-assessment that determines tocolytic therapy is no longer indicated (according to investigator's medical discretion), abnormal levels of alanine aminotransferase (ALT) or bilirubin (if results are available), or a clinically significant abnormal finding on an ECG cannot be dosed and should be withdrawn from the study. The reasons for not dosing a subject will be recorded in the eCRF and source documents. Subjects who are withdrawn prior to receiving randomized IP will not be followed.

A nonreassuring fetal heart rate is defined as either unresolved Category 3 tracings (including either [1] the absence of baseline fetal heart rate variability and any of the following: recurrent late decelerations, recurrent variable decelerations, or bradycardia; or [2] sinusoidal pattern) or at the investigator's discretion.

Dosing may be started before local liver function test results are available; however, if local laboratory results are available before the start of dosing and ALT is $>2 \times$ the upper limit of normal (ULN) or bilirubin is $>1.5 \times$ ULN ($>35\%$ direct bilirubin), the subject should not be dosed and should be withdrawn from the study. An isolated bilirubin $>1.5 \times$ ULN is acceptable if bilirubin is fractionated and direct bilirubin is $<35\%$. See Section 6.3.1 for liver stopping criteria for management of abnormal test results that become available after the start of dosing.

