19. Electronic fetal monitoring is required for a minimum of 6 hours from the start of the infusion or from the start of a dose increase. As long as the fetal heart rate pattern is consistently reassuring throughout the required 6-hour duration of monitoring and the contraction frequency is ≤ 2 in a 30-minute window within the last hour of monitoring, continuous monitoring may be discontinued and nonstress tests initiated at a minimum of every 8 hours and as needed. Electronic fetal monitoring, including the fetal heart rate and fetal heart rate category, will be recorded in the eCRF with maternal vital signs. Any fetal heart rate assessment of Category II or III will be reported as an AE of special interest on a specified eCRF (details in Section 6.3.12.3).
20. If the subject has not delivered at the end of the Inpatient Randomized Treatment Phase, fetal heart rate (fetal Doppler heart rate or cardiotocography are both acceptable) will be recorded at the face-to-face post-infusion assessment visit. Any fetal heart rate assessment of Category II or III will be reported as an AE of special interest on a specified eCRF (details in Section 6.3.12.3).
21. During the Delivery Phase, fetal heart rate just prior to delivery will be collected, if available, from review of delivery records. Any fetal heart rate assessment of Category II or III will be reported as an AE of special interest on a specified eCRF (details in Section 6.3.12.3).
22. Maternal and neonatal health care resource use may include, but is not limited to, neonatal complications requiring intensive or specialized care, neonatal hospital readmission, and neonatal ambulatory surgery.
23. PK samples will be taken at the following sampling windows (relative to the start of the infusion): 2 to 4 hours, 10 to 14 hours, 22 to 26 hours, and 48 to 54 hours. In addition, a PK sample should be taken at the onset of any maternal or fetal SAE that occurs within 12 hours after completion or discontinuation of IP. A maternal blood sample should be collected at the same time as the cord blood sample (see Section 6.5.1) if the sample time does not already coincide with one of the PK sampling windows.
24. In subjects who deliver at an investigative center within 12 hours following completion or discontinuation of the IP, the cord blood sample will also be divided for PK analysis as well as genetic (if additional consent is provided; see [Appendix 1](#)) and biomarker analyses.

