6.1. Critical Assessments Prior to Investigational Product Administration

The following assessments are required before dosing (i.e., before initiating randomized treatment):

- Electronic fetal monitoring to confirm that the fetal heart rate pattern remains reassuring
- Re-assess that tocolytic therapy is still indicated, according to the investigator's medical discretion.
- Liver function tests from a local laboratory to confirm that ALT is not $\geq 2 \times$ ULN OR bilirubin is not $> 1.5 \times$ ULN ($> 35\%$ direct bilirubin), if available (see Section 6.3.1). An isolated bilirubin $> 1.5 \times$ ULN is acceptable if bilirubin is fractionated and direct bilirubin is $< 35\%$. Dosing may be started prior to the availability of these results.
- Electrocardiogram that is interpreted by the investigator to not have any significant abnormalities that may place the subject at risk for a cardiopulmonary complication during the study

If the fetal heart rate pattern is nonreassuring, tocolytic therapy is no longer indicated, levels of ALT or bilirubin are abnormal (if results are available), or the ECG has been interpreted to have clinically significant abnormalities, the subject cannot be dosed and will be withdrawn from the study (see Section 4.4.1).

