6.3.2.1. Definition of an AE

Any untoward medical occurrence in a patient or clinical investigation subject, temporally associated with the use of a medicinal product, whether or not considered related to the medicinal product.

Note: An AE can therefore be any unfavorable and unintended sign (including an abnormal laboratory finding), symptom, or disease (new or exacerbated) temporally associated with the use of a medicinal product. For marketed medicinal products, this

also includes failure to produce expected benefits (i.e., lack of efficacy), abuse, or misuse.

Events meeting the definition of an AE include:

- Exacerbation of a chronic or intermittent pre-existing condition including either an increase in frequency and/or intensity of the condition
- New conditions detected or diagnosed after study treatment administration even though it may have been present prior to the start of the study
- Signs, symptoms, or the clinical sequelae of a suspected interaction
- Signs, symptoms, or the clinical sequelae of a suspected overdose of either study treatment or a concomitant medication (overdose per se will not be reported as an AE/SAE) unless this is an intentional overdose taken with possible suicidal/self-harming intent. This should be reported regardless of sequelae

“Lack of efficacy” or “failure of expected pharmacological action” per se will not be reported as an AE or SAE. However, the signs and symptoms and/or clinical sequelae resulting from lack of efficacy will be reported if they fulfill the definition of an AE or SAE.

Events that **do not** meet the definition of an AE include:

- Medical or surgical procedure (e.g., endoscopy, appendectomy); the condition that leads to the procedure is an AE
- Situations where an untoward medical occurrence did not occur (social and/or convenience admission to a hospital)
- Anticipated day-to-day fluctuations of pre-existing disease(s) or condition(s) present or detected at the start of the study that do not worsen

The disease/disorder being studied, or expected progression, signs, or symptoms of the disease/disorder being studied, unless more severe than expected for the subject’s condition.

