8.2.6.2. Fetal Heart Rate

Summaries for fetal heart rate will be performed using the Maternal Safety Population.

A table will summarize categorical fetal heart rate results by treatment group during treatment phase and post-treatment phase. Categories to be presented are Category I, II and III based on ACOG guidelines [ACOG, 2009].

All fetal heart rate data by subject will be presented in a listing.

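### No planned table compares fetal tracing category with the pre-dose category, so an unchanged Category II pattern shows as an on-treatment result and can be counted as an AE of special interest

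*Protocol*

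**What the plan says.** **Reporting rule.** Protocol 6.3.12.3: "Any fetal heart rate assessment of Category II or III according to the following criteria and based on ACOG guidelines [ACOG, 2009] will be reported". Each such report is an AESI, entered on its own form and also on the AE or SAE form. Time and Events footnotes 19 to 21 repeat this for treatment, the post-infusion visit and delivery: "Any fetal heart rate assessment of Category II or III will be reported as an AE of special interest on a specified eCRF". None of these texts refers to the pre-dose category.

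**Before dosing.** Protocol 6.1 requires "Electronic fetal monitoring to confirm that the fetal heart rate pattern remains reassuring" and names no category. Protocol 4.4.1.1 gives the definition: "A nonreassuring fetal heart rate is defined as either unresolved Category 3 tracings", or investigator discretion. Section 6.3.12.3 links a reassuring result to Category I, but only for the nonstress test.

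**Recording.** Under 6.3.12.3 the heart rate and category "should be recorded in the eCRF at approximately the same time that maternal vital sign measurements are collected". Section 6.3.12.2 includes Screening among the vital sign time points.

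**General AE rules.** Protocol 6.3.2.1 lists among things that are not AEs: "Anticipated day-to-day fluctuations of pre-existing disease(s) or condition(s) present or detected at the start of the study that do not worsen". Section 6.3.8 allows occurrences between consent and dosing to be entered as medical history. SAP 8.2.3 restricts AE tables to events that start at or after first treatment, and 8.2.3.6 handles AESIs in the same way.

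**Planned outputs.** SAP 8.2.6.2: "A table will summarize categorical fetal heart rate results by treatment group during treatment phase and post-treatment phase". This is Table 3.424. SAP Table 5 gives fetal heart rate the same four marks as laboratory tests and maternal vital signs, which include change-from-baseline summaries. Appendix 11, the only output list, keeps those summaries for laboratory tests and vital signs and has none for fetal heart rate. SAP section 9 does not list it as dropped.

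**The concern.** Protocol 6.3.12.3 itself warns that Category II can be a sizeable part of the tracings seen in practice. A fetus that is Category II before the infusion and stays so tells us nothing about the drug, yet it looks the same in the planned tables as a fetus that moves from I to II during the infusion. Such fetuses are expected in equal proportion in both arms. They raise both percentages and pull the ratio and the difference between arms toward no effect. Of the three fetal AESIs, tracing category is the one assessed repeatedly during the infusion, so a weaker comparison here makes a fetal effect harder to see among 97 enrolled women.

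**Working it through.** The documents give no rate, power or sample size for tracing events, so there is no stated figure to reproduce.

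**1. Follow one fetus that is Category II before and after dosing.**

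- *Table 3.424* is built from recorded categories, not AE forms. SAP 11.3.1 assigns phase by date and time, so the post-dose assessment is on-treatment and counts as Category II. The AE filters do not apply to this table.
- *Table 3.171* depends on what the site records:
  - Onset entered as the first post-dose tracing: counted.
  - Onset entered before dosing, on an earlier date: excluded by SAP 8.2.3.
  - Onset entered before dosing, on the same date: on-treatment, because SAP 11.3.3 compares dates without times.
  - Partial onset date that imputes to before dosing: moved to the first treatment date (SAP 11.6.2.2) and counted.
  - Treated as pre-existing and unchanged, or as medical history: not counted.

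Protocol 6.3.2.1 points both ways. It excludes pre-existing conditions that do not worsen, but includes conditions first detected after dosing that may have been there earlier.

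**2. Size of the dilution.** Let b be the share that is Category II before dosing, q the share of those that persist, and p the rate of new events. If persisting patterns are counted:

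- rate shown = b[q + (1 − q)p] + (1 − b)p = p + bq(1 − p)
- difference shown = true difference × (1 − bq)

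b, q and p are all assumptions. For p = 10% against 20% (difference 10 points, ratio 2.0):

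| b | q | Shown | Difference (points) | Ratio |
|---|---|---|---|---|
| 0 | – | 10% v 20% | 10 | 2.00 |
| 5% | 1 | 14.5% v 24% | 9.5 | 1.66 |
| 20% | 0.5 | 19% v 28% | 9 | 1.47 |
| 20% | 1 | 28% v 36% | 8 | 1.29 |
| 40% | 1 | 46% v 52% | 6 | 1.13 |

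**3. What a baseline-aware display shows.** Take b = 20%, q = 1 and, for simplicity, no II-to-III moves. A row for tracings worse than pre-dose, over all dosed women, gives 0.8 × 10% = 8% against 0.8 × 20% = 16%. The ratio is 2.0 again, but the difference is still 8 points. Among fetuses that were Category I before dosing, which only a shift table identifies, the figures are 10% against 20%.

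**4. Scale.** Nominal two-sided 5% power at b = 20%, q = 1, all women as written against fetuses that were Category I before dosing: 0.34 against 0.62 at the planned 165 per arm, and 0.13 against 0.23 at about 48 per arm (97 enrolled). No formal safety test is planned, so these figures indicate scale only.

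**The case against.** The strongest reply is that the AESI table is protected. An AESI is also an AE with an onset date, SAP 8.2.3 admits only events starting at or after first treatment, and Protocol 6.3.2.1 and 6.3.8 steer unchanged or earlier conditions away from the AE form. This stands in part: one cannot say that every pre-existing pattern will be counted in Table 3.171. But the tracing rule is specific, says "any" and does not refer to those general rules, and the date-only cut-off lets same-day onsets through. None of this touches Table 3.424.

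Other points carry weight:

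- The exclusion criteria remove fetal compromise and nonreassuring status, and the pattern must still be reassuring before dosing. The protocol's remark about Category II frequency concerns clinical care generally, so the share among dosed women may be small.
- Capture at Screening is probable, not certain. The footnote on the Screening cell concerns only the bar to dosing; the footnote on recording the category is attached to the treatment days and retreatment.
- SAP 11.4.2.1 already defines baseline generally as the latest pre-dose assessment, and Listings 56 and 123 show individual data. A listing does not give a comparison by arm.
- The column positions in SAP Table 5 are hard to read. The evidence is that fetal heart rate carries the same marks as laboratory tests and vital signs, while the AE rows carry fewer.

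**Conclusion.** The point holds as a loss of sensitivity. Any unchanged pre-dose Category II pattern will appear as an on-treatment result in Table 3.424 and can appear as an AESI in Table 3.171, and no planned table compares post-dose with pre-dose category. The difference between arms shrinks by the factor (1 − bq). The size cannot be fixed from the documents: under the assumed rates, a true ratio of 2.0 becomes anything from 2.0 (b = 0) to 1.13 (b = 40%, full persistence). The calculation assumes that b and q are the same in both arms and that new events arise at the same rate within an arm whatever the pre-dose category.

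A reader might infer three stronger things that the documents do not support:

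- *That all pre-existing patterns are counted as AESIs.* The general AE rules point the other way, and the conflict is unresolved.
- *That a real fetal effect is known to be masked.* This needs a pre-dose Category II share that the documents do not give.
- *That the comparison is biased between arms.* Randomisation balances the pre-dose share in expectation, and safety is only described (Protocol 8.3.5.2).

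A move from Category II to III is a true worsening and should remain an event. The case for acting is that the better display is cheap.

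**What to change.** Before unblinding:

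1. Make Table 3.424 a shift table: last pre-dose category by worst post-dose category, by arm and phase, with a row for a missing pre-dose category.
2. In Table 3.171, keep the count of any Category II or III and add a row beside it for tracings worse than the last pre-dose category, so that II to III still counts.
3. In SAP 11.3.3, use date and time for the pre-treatment cut-off of fetal tracing events.
4. State in the SAP how the tracing rule (Protocol 6.3.12.3 and footnotes 19 to 21) fits with Protocol 6.3.2.1 and 6.3.8 and SAP 8.2.3.
5. Reconcile the wording on reassuring and nonreassuring patterns in Protocol 4.4.1.1, 6.1 and 6.3.12.3. No change to the dosing rule is proposed.

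The cost is one reprogrammed table, one added row and a short SAP clarification. Site reporting does not change. The downside is that some women may fall in the missing row if the Screening category was not captured.
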